Site Visit		X	X	X	X	X					Site visit is preferred after discharge, but telephone visit is acceptable after discharge and should include collection of concomitant medications, adverse events, COVID-19 clinical symptoms, and Clinical Status Assessment. Failure to conduct activities that cannot be reasonably performed over the telephone will not be considered a protocol deviation.
Telephone Visit							X	X			
Prespecified medical history: comorbidities	X										Includes comorbidities such as, but not limited to, diabetes, hypertension, cardiovascular disease, underlying pulmonary disease.
Prespecified medical history: COVID-19	Х										Includes COVID-19 diagnosis date and onset of COVID-19 symptoms.
Prior treatments of special interest within last 2 weeks	X										Includes NSAIDs, antivirals, antibiotics, antimalarials, corticosteroids, herpes zoster vaccine, immunosuppressive medications.
Substance use (tobacco use)	Х										
Concomitant medications	Х	Х	Х	Х	Х	Х	Х	Х	Х		Assess daily. Includes medications of interest: background therapy, supportive care, sedating/paralytic drugs, and VTE prophylaxis.
Adverse events (AEs)	X	Х	Х	Х	Х	Х	Х	Х	Х		Assess daily. AE collection begins when ICF is signed. For infections and VTEs, additional data are collected (Section 8.3.6).
COVID-19 clinical symptoms	Х	Х	Х	Х	Х	Х	Х	Х	Х		Assess daily while hospitalized and on day of visits after discharge.

Study day	1	4	7	10	14	28	Follow-up (28 Days after Last Dose)	Follow-up Day 60	ETV	Unsched uled	Comments
Interval tolerance (days)	≤3	_	_	_	_	_	±4	+7	_	_	If patient is discharged from hospital, the study visit may include a visit interval tolerance (window) of $\pm 2$ at Study Day 4, Day 7, Day 10, Day 14, and Day 28.
Site Visit		X	X	X	X	X					Site visit is preferred after discharge, but telephone visit is acceptable after discharge and should include collection of concomitant medications, adverse events, COVID-19 clinical symptoms, and Clinical Status Assessment. Failure to conduct activities that cannot be reasonably performed over the telephone will not be considered a protocol deviation.
Telephone Visit							X	X			
Clinical Assessments											
Height	Х										May be as measured or reported.
Weight	Х										
Vital signs	X	X	Х	X	X	X			X		Assess and document daily while hospitalized. Includes: respiratory rate and oxygen saturation, blood pressure, body temperature, heart (pulse) rate. See Section 8.2.1.

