# 2.2. Background

In December 2019, a life-threatening infectious disease first observed in Wuhan, China, and later identified as COVID-19 has rapidly spread, causing a global pandemic. According to the World Health Organization (WHO), as of 20 April 2020, 2,314,621 confirmed cases have been reported worldwide with 157,847 deaths (WHO COVID-19 Situation Report 91).

COVID-19 belongs to the coronavirus family of single-stranded RNA viruses that can cross species barriers and can cause illness ranging from the common cold to more severe diseases such as SARS and MERS. Transmission of COVID-19 is believed to occur through respiratory droplets from coughing and sneezing. The pathogenesis is unclear, but the virus seems capable of producing an excessive immune reaction, which results in extensive tissue damage (Rothan and Byrareddy 2020).

The majority of individuals infected with COVID-19 experience a mild respiratory disease generally affecting the lower airways; symptoms usually appear after an incubation period of approximately 5 days. The most common symptoms at onset include fever, fatigue, and dry cough. Other signs and symptoms include myalgia, headache, diarrhea, nausea, dyspnea, lymphopenia, prolonged thrombin time, elevated lactate dehydrogenase, elevated alanine transaminase, and creatine kinase, and bilateral infiltrates on chest imaging. Patients can deteriorate rapidly. The median time from first symptoms to hospitalization is 7 days (Wang D et al. 2020).

Huang et al. (2020) reported that 27% of hospitalized patients diagnosed with COVID-19 infection in China developed ARDS after 9 days from onset of symptoms requiring oxygen therapy and intensive care. Some patients have laboratory evidence of a severe inflammatory response, similar to the cytokine release syndrome, with persistent fever, elevated inflammatory markers (hs-CRP, D-dimer, ferritin), and multiple organ dysfunction (Guan et al. 2020; Chen T et al. 2020). The major complications during hospitalization include ARDS, arrhythmia, and shock. Disease severity and mortality appears to be associated with those over the age of 70 and individuals with underlying comorbidities such as diabetes, hypertension, cardiovascular disease, chronic renal disease, and chronic lung disease (Chen N et al. 2020; Guan et al. 2020; Rothan and Byrareddy 2020; Wang W et al. 2020).

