## 9.4.2. Primary Endpoint

The primary comparison of interest is the proportion of patients who die or require non-invasive ventilation/high-flow oxygen or invasive mechanical ventilation (including ECMO) by Day 28. Patients on non-invasive ventilation/high-flow oxygen at baseline will be counted toward this endpoint if they progressed to invasive mechanical ventilation. Treatment comparisons between baricitinib 4-mg QD + background therapy and placebo + background therapy will be made using logistic regression with baseline stratification factors and treatment group in the model. The primary objective will be assessed in two populations. The primary endpoint will be met if either of the two tests described in Section 9.1 is statistically significant.

If the sample size is increased as a result of the interim analysis, the Cui, Hung, and Wang (CHW) procedure (Cui et al. 1999) will be applied to the endpoints to control the type I error at a one sided  $\alpha$ =0.025 significance level. The CHW method ensures strong control of type I error when the sample size is increased in a data dependent manner.

If the sample size is increased as a result of the interim analysis, an unadjusted point estimate for the primary efficacy analysis will be calculated and reported. A median unbiased point estimate and a stage-wise adjusted confidence interval for the primary efficacy analysis will be calculated and reported based on the approach described by Brannath and colleagues (Brannath et al. 2009) to assess sensitivity of the point estimate.

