### 6.1.4. Baseline Stratification Variables

Throughout the SAP, when baseline stratification variables are referred to, they include the following categorical variables:

- baseline disease severity (ordinal scale [OS] 4, OS 5, OS 6),
- age (<65 years, ≥65 years),
- region (US, Europe, rest of world) and
- dexamethasone and/or other systemic corticosteroid used at baseline for primary study condition (Yes/No).

If any of these are redundant for a particular model they will be dropped.

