### **6.2.1. Logistic Regression Model**

Treatment comparisons of discrete/binary efficacy variables between treatment groups will be made using a logistic regression analysis adjusted for baseline stratification variables (Section 6.1.4). The p-value and odds ratio with 100(1- $\alpha$ )% confidence interval (CI) from the logistic model will be reported.

Point estimates for proportions and difference in proportions will be presented. Confidence intervals and p-values for the estimates of the differences of the proportions and will be presented. For last-observation-carried-forward (LOCF) analyses the CIs will be based on the Newcombe-Wilson method without continuity correction. For multiple imputation analyses, percentages will be based on the observed percentages; CIs will be based on the Wald method without continuity correction.

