### **6.8.3. Historical Illness and Preexisting Conditions**

Historical illnesses are defined as those conditions recorded in the Preexisting Conditions and Medical History electronic case report form (eCRF) or from the Prespecified Medical History: Comorbidities eCRF with an end date prior to the informed consent date. The number and percentage of patients with selected historical diagnoses will be summarized by treatment group using the ITT population. Historical diagnoses will be categorized using the Medical Dictionary for Regulatory Activities (MedDRA; most current available version) algorithmic Standardized MedDRA Queries (SMQs) or similar pre-defined lists of Preferred Terms (PTs) of interest.

Preexisting conditions are defined as those conditions recorded in the Pre-existing Conditions and Medical History eCRF, or the Prespecified Medical History: Comorbidities eCRF with a start date and time prior to the informed consent and with a stop date that is after the informed consent date or have no stop date (ongoing). Adverse events (AEs) are recorded in the eCRFs. For events recorded on the AE page, we considered it as a preexisting event if its onset date was before the first dose date. For events occurring on the day of the first dose of study treatment, the date and time of the onset of the event will both be used to determine if the event was preexisting. Conditions with a partial or missing start date (or time if needed) will be assumed to be 'not preexisting' unless there is evidence, through comparison of partial dates, to suggest otherwise. Preexisting conditions will be categorized using the SMQs or similar predefined lists of PTs of interest. Frequency counts and percentages of patients with selected preexisting conditions will be summarized by treatment group using the ITT population.

The number and percentage of participants using preferred terms of prior medications will be presented.

The following historical illness and preexisting conditions will be presented:

- preexisting comorbid conditions:
  - none, any
- preexisting comorbid conditions of interest
  - obesity
  - diabetes (Type I and Type II)
  - chronic respiratory disease
  - hypertension

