## 6.14. Subgroup Analyses

For primary and gated secondary endpoints, following subgroup analysis will be conducted:

- baseline disease severity:
  - hospitalized not requiring supplemental oxygen, requiring ongoing medical care (OS 4)
  - hospitalized requiring supplemental oxygen by prongs or mask (OS 5)
  - hospitalized requiring noninvasive ventilation or high-flow oxygen (OS 6)
  - OS 5 and OS 6 combined
- baseline steroid use: dexamethasone and/or other systemic corticosteroid used at baseline for primary study condition (Yes/No)
- baseline remdesivir use (Yes/No)

The following subgroups categorized into disease-related characteristics and demographic characteristics will be evaluated for primary endpoint. These analyses may also be conducted selectively on key secondary endpoints if applicable:

- patient demographic and characteristics subgroups:
  - gender (male, female)
  - age group (<65, ≥65)
  - baseline weight (<60 kg, ≥60 to <100 kg, ≥100 kg)
  - baseline BMI (<25 kg/m^2, ≥25 to <30 kg/m^2, ≥30 kg/m^2)
  - race (American Indian or Alaska Native, Asian, Black or African American, Native Hawaiian or Other Pacific Islander, White, Multiple)
  - baseline renal function status: impaired (eGFR <60 mL/min/1.73 m^2) or not impaired (eGFR ≥60 mL/min/1.73 m^2)
- geographic region subgroups:
  - region (US, Europe, Rest of World)
- baseline disease-related characteristics subgroups:
  - baseline disease duration of symptoms prior to enrollment:<7 days, ≥7 days

- preexisting comorbid conditions of interest: none, any

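### The Population 1 models could also adjust for pre-existing comorbidity: the current primary model is valid, and the gain in power would be modest

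*SAP*

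**What the plan says.** SAP 6.1.4 fixes the covariate set for the whole plan: "when baseline stratification variables are referred to, they include the following categorical variables". The list is baseline OS category (4, 5, 6), age split at 65, region, and systemic steroid use at baseline. SAP 6.2.1 says binary comparisons "will be made using a logistic regression analysis adjusted for baseline stratification variables (Section 6.1.4". SAP 6.2.2 (ANOVA) and 6.2.4 (proportional odds) point to the same list. Protocol 9.4.2 agrees for the primary endpoint: "logistic regression with baseline stratification factors and treatment group in the model".

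Comorbidity appears elsewhere in the plan:

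- Protocol 2.2: "Disease severity and mortality appears to be associated with those over the age of 70 and individuals with underlying comorbidities such as diabetes, hypertension", then cardiovascular, chronic renal and chronic lung disease. No effect size is given.
- Protocol 1.3, Day 1 medical history: "Includes comorbidities such as, but not limited to, diabetes, hypertension, cardiovascular disease, underlying pulmonary disease".
- SAP 6.14, subgroups of the primary endpoint: "preexisting comorbid conditions of interest: none, any".
- SAP 6.8.3: "Conditions with a partial or missing start date (or time if needed) will be assumed to be" not pre-existing, unless the partial dates suggest otherwise. Almost every patient therefore receives a value.

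No primary, supportive or sensitivity analysis in SAP Table KHAA.6.5 or Section 6.11.4 adjusts the overall treatment effect for comorbidity. The subgroup model in SAP 6.14 contains it, but only with a treatment interaction and, per Table KHAA.6.12, with LOCF rather than the multiple imputation used for the primary analysis.

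**The concern.** The primary endpoint is progression or death, and the protocol itself links comorbidity to severity and mortality. Comorbidity is not a randomization factor, so neither the design nor the model guards against a chance imbalance in it. Age in the model may not stand in for it fully: the model cuts age at 65, while Protocol 2.2 places the raised risk above 70.

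Adjusting for a baseline variable that predicts the outcome raises the power of the test of the conditional odds ratio. In the ANOVA models it lowers residual variance. The data are already collected and the variable already derived. At stake is a small amount of power, not the validity of the trial.

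**Working it through.** **1. Reproduce the plan's power.** The last power statement with all inputs given is for amendment D (Protocol 9.2): 1000 patients, 25% placebo events, two-sided alpha 0.05, power 47% for a 5-point difference and 83% for 7.5 points.

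Power = Φ[(Δ − z·SE0)/SE1], with SE0 pooled and SE1 unpooled.

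- 25% vs 20%, 500 per arm: SE0 = √(2 × 0.225 × 0.775/500) = 0.0264 and SE1 = √((0.1875 + 0.16)/500) = 0.0264. Power = 47.3%.
- 25% vs 17.5%: SE0 = 0.0259, SE1 = 0.0258. Power = 82.7%.

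Both agree with the plan. The amendment E figures (81% and 54% at 1400) do not reproduce at a 25% placebo rate with every patient at OS 5 or 6 (91.8% and 69.6%). They depend on a control rate or an OS 4 share that is not stated. The comparisons below are therefore relative and do not use those two figures.

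**2. Starting point for Population 1.** With 700 per arm, 25% placebo events and alpha 0.99 × 0.05 = 0.0495 two-sided (weight from SAP 6.6), the same formula gives 92.9% for a 7.5-point difference and 67.9% for 5.4 points.

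**3. Effect of adding comorbidity.** The documents give neither its prevalence nor its association with the endpoint, so both are assumed. With p0 and p1 the event rates without and with comorbidity, π the prevalence and a pooled event rate of (25% + 17.5%)/2 = 21.25%:

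R² = (p1 − p0)² π(1 − π)/(0.2125 × 0.7875); effective-N ratio = 1/(1 − R²).

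Example, prevalence 50% and odds ratio 3: p0 = 0.125, p1 = 0.300, R² = 0.175² × 0.25/0.1673 = 0.0458. The ratio is 1.048, or 67 of 1400 patients.

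The formula was checked by paired simulation of the logistic model with and without the comorbidity term. It used N = 1400 and 2,500 runs per cell, and measured the gain by the squared ratio of mean z. Assumed: OS 4 12%, OS 6 27%, age 65 or over 35%, steroid use 70%, moderate covariate effects, comorbidity 15 points more frequent at 65 or over, no missing data.

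| Prevalence | Odds ratio | Gain, formula | Gain, simulated (7.5 / 5.4 points) | Power at 7.5 (from 92.9%) | Power at 5.4 (from 67.9%) |
|---|---|---|---|---|---|
| 50% | 1.5 | +0.7% | +0.7% / +0.6% | 93.1% | 68.2% |
| 50% | 2 | +2.0% | +2.1% / +2.2% | 93.4% | 68.7% |
| 50% | 3 | +4.8% | +5.0% / +5.0% | 94.0% | 69.9% |
| 80% | 1.5 | +0.4% | +0.4% / +0.3% | 93.0% | 68.0% |
| 80% | 2 | +1.0% | +0.9% / +0.9% | 93.2% | 68.3% |
| 80% | 3 | +2.1% | +2.0% / +1.8% | 93.4% | 68.7% |

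The simulated range of +0.3% to +5.0% is about 4 to 71 patients. With an odds ratio of 1 there is no gain. At 90% prevalence the formula gives +0.2% to +1.0%. Ten of the twelve formula power gains are below one point. The simulated paired change in power over these cells ran from −0.2 to +3.3 points, with simulation error up to 0.5.

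**4. Where the gain comes from.** At prevalence 50%, odds ratio 3 and a 7.5-point difference, the log-odds ratio moves from −0.4715 to −0.4958 and its standard error rises from 0.1362 to 0.1397. The ratio of z values is 3.549/3.462 = 1.025, squared 1.051. The estimate moves away from zero faster than the standard error grows.

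**5. Population 2.** Its size is not given, so 100, 200 and 560 were assumed (560 = 40% of 1400, from the 60% steroid share in Protocol 9.2). With odds ratio 2 the effective-N ratio is 1.01 to 1.03. At 100 patients an uninformative covariate gives 0.99 to 1.00, and 4-12% of fits were unstable in one or both models.

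**The case against.** The strongest reply is that nothing here is wrong. Protocol and SAP agree on one model, adjusting for the randomization factors is sound, and type I error is controlled. That stands.

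The prognostic basis is also thin. Protocol 2.2 is hedged and concerns COVID-19 generally. Under the current criteria (Protocol 5.1), patients already need oxygen and have a raised inflammatory marker, and OS and age carry part of the signal. The conditions of interest in SAP 6.8.3 include obesity, which Protocol 2.2 does not list, and omit cardiovascular and chronic renal disease, which it does. History may come from verbal interview, and missing start dates default to not pre-existing. Misclassification of this kind would dilute the gain. All of this stands and is why the size is given as a range with zero at one end.

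Comorbidity is also partly handled: it is tabulated by arm and is a subgroup of the primary endpoint. Neither gives a comorbidity-adjusted primary estimate.

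A reader might infer more than the documents support:

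- **That precision is being lost.** For the odds ratio the standard error rises slightly. Under multiple imputation the risk-difference interval uses observed percentages and the Wald method (SAP 6.2.1), so it gains nothing.
- **That the change is free.** It departs from Protocol 9.4.2 and adds a factor to the Fisher's-exact fallback in Protocol 9.4.1 (fewer than five responders in any category). In Population 1 the fallback is unlikely: at an assumed 90% prevalence, 140 of 1400 patients have no comorbidity, and an assumed 10% event rate gives 14 events.
- **That small Population 2 benefits most.** It is smaller than anticipated (SAP Section 3), has 0.01 of the alpha weight, and step 5 shows little gain and some instability.
- **That all key secondaries benefit.** Time to recovery and mortality use an unstratified log-rank test (SAP 6.2.3, Table KHAA.6.5), which takes no covariates.

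**Conclusion.** The point holds as a small optional improvement, confined to Population 1. Comorbidity is omitted although the protocol treats it as associated with outcome and the SAP already derives it. If it predicts the endpoint beyond OS and age, adding it raises power for the odds ratio by the equivalent of about 0.3% to 5% more patients, at an assumed prevalence of 50-80% and an assumed odds ratio of 1.5-3. If it does not, nothing is gained. Residual variance in the ANOVA key secondaries (ventilator-free days, duration of hospitalization) would also fall; the documents give no figures from which to size that. The omission is not an error and does not threaten the primary conclusion.

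**What to change.** Before unblinding, and chosen by staff who have seen no unblinded data:

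1. Leave the definition in SAP 6.1.4 unchanged. Comorbidity is not a stratification variable, and adding it there would carry it into the MMRM and every subgroup interaction model.
2. Add a line to SAP 6.2.1, 6.2.2 and 6.2.4: the Population 1 logistic, ANOVA and proportional-odds models also include pre-existing comorbid condition (none/any, as derived for 6.14). State which conditions the flag counts.
3. Keep the model with stratification factors only as a supportive analysis.
4. Leave the Population 2 model and the log-rank tests as they are.

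Cost: one extra parameter and a documented departure from the covariates named in Protocol 9.4.2. No new data are needed. Few or no patients should fall under the missing-covariate exclusion in SAP 6.1, because of the default for missing dates.

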Physical examination	X										The complete physical exam is performed if feasible (excludes pelvic, rectal, and breast exams). An assessment of risk factors for tuberculosis (TB) is included (Section 8.2.2).
Symptom-directed physical examination		Х	Х	Х	Х	Х			Х		See Section 8.2.2.
Chest imaging (CT scan or x-ray) (local)	X			Х					Х	Х	Assessed by radiologist or pulmonologist (Section 8.2.4). Documentation of hospital-based imaging prior to study entry, obtained up to 24 hours prior to study entry is acceptable.

Study day	1	4	7	10	14	28	Follow-up (28 Days after Last Dose)	Follow-up Day 60	ETV	Unsched uled	Comments
Interval tolerance (days)	≤3	_	_	_		_	±4	+7	_	_	If patient is discharged from hospital, the study visit may include a visit interval tolerance (window) of $\pm 2$ at Study Day 4, Day 7, Day 10, Day 14, and Day 28.
Site Visit		X	X	X	X	X					Site visit is preferred after discharge, but telephone visit is acceptable after discharge and should include collection of concomitant medications, adverse events, COVID-19 clinical symptoms, and Clinical Status Assessment. Failure to conduct activities that cannot be reasonably performed over the telephone will not be considered a protocol deviation.
Telephone Visit							Х	Х			
12-lead ECG (local)	Х										Performed and assessed locally. Documentation of hospital-based ECG prior to study entry, up to 24 hours prior to study entry is acceptable (Section 8.2.3).
Clinician-Administered Assessments Paper											
Clinical Status Assessment	Х	Х	Х	X	Х	Х		Х	Х		Document daily through Day 29. Includes status of oxygen/life support procedures and proning.
Assessment for the NEWS	Х	Х	Х	Х	Х	Х			Х		Document daily.
Laboratory Tests and Sample Collections											For laboratory tests and sample collections, the timing can be +1 day or -1 day from the designated day, unless otherwise specified.
Hematology	Х	х	х	x	х	x			Х	Х	Performed locally. Tests performed in the 24 hours prior to study entry will be accepted for determination of eligibility. Unscheduled collection, if clinically warranted, will be entered into the eCRF.

Study day	1	4	7	10	14	28	Follow-up (28 Days after Last Dose)	Follow-up Day 60	ETV	Unsched uled	Comments
Interval tolerance (days)	≤3	_	_	_	_	_	±4	+7	_	_	If patient is discharged from hospital, the study visit may include a visit interval tolerance (window) of $\pm 2$ at Study Day 4, Day 7, Day 10, Day 14, and Day 28.

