#### National Early Warning Score (NEWS)

In this study, because the scores for the NEWS parameters will be derived from data already entered into the eCRF, no additional NEWS-specific data entry will be required.

The National Early Warning Score (NEWS) is used to detect and report changes in illness severity in patients with acute illness. The score is determined from six physiological parameters readily measured over time in hospitalized patients:

- respiration rate
- oxygen saturation
- temperature
- systolic blood pressure
- heart (pulse) rate, and
- level of consciousness, as measured by AVPU.

A score is assigned to each parameter, with the magnitude of the score representing the extremity of variation from the norm. A weighting score is added for patients needing supplemental oxygen (oxygen delivery by mask or nasal cannula). The aggregate score is reflective of the patient's status (Royal College of Physicians 2012).

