## 8.2.1. Vital Signs

Vitals signs (body temperature, blood pressure, heart [pulse] rate, respiration rate, oxygen saturation) will be assessed and documented daily, and as clinical indicated, and entered into the eCRF as specified in the SoA (Section 1.3) and as clinically indicated.

These include the minimum/maximum vital signs daily (including temperature, respiratory rate, oxygen saturation).

The most recent measurements prior to study drug administration will be used to calculate the NEWS. Vital signs should be performed at approximately the same time each day.

Additional vital signs may be measured during the study visits if warranted, as determined by the investigator and/or appropriate designee.

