### 6.1.2. Definition of Study Baseline

Unless otherwise specified, for efficacy and health outcomes, baseline is defined as the last nonmissing assessment recorded on or prior to, the first date that clinical status is assessed.

Baseline for safety analyses is described in [Table KHAA.6.8](#).

Change from baseline will be calculated as the visit value of interest minus the baseline value. If a baseline value or the value at the visit is missing for a variable, then the change from baseline is defined as missing.

The baseline of vital signs is defined as the vital signs collated at Day 1 from the case report form (CRF) Assessment for the National Early Warning Score (NEWS) (AVPU1001\_VS1001\_F1). The post baseline vital signs for analyses other than NEWS is defined as vital signs collated from CRF Vital Signs: Minimum and Maximum (VS1001).

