### 6.11.1. Primary Outcome and Methodology

The primary comparison of interest is the proportion of patients who die or require non-invasive ventilation/high-flow oxygen or invasive mechanical ventilation (including ECMO) by Day 28. The primary comparison will be performed on two different populations:

- Population 1 – all randomized patients
- Population 2 – patients who, at baseline, require oxygen supplementation and are not receiving dexamethasone or other systemic corticosteroids for the primary study condition.

Patients on non-invasive ventilation/high-flow oxygen at baseline will be counted toward this endpoint if they progressed to invasive mechanical ventilation. Treatment comparisons between baricitinib 4-mg QD + background therapy and placebo + background therapy will be made using logistic regression with baseline stratification factors and treatment group in the model.

- Pr.V: Proportion of patients who died or require non-invasive ventilation/high-flow oxygen or invasive mechanical ventilation (including ECMO) by Day 28. For patients who start with ventilation at baseline, the patients need to be worsening in symptom (at least 1-point worsening in NIAID-OS) to be counted.

For the primary comparison involving two different populations, the alpha will be split between the two populations such that 99% of alpha is assigned to Population 1 and the rest to Population 2. The primary endpoint will be met if any one or both of these two populations show a significant treatment effect.

If the sample size is increased as a result of the interim analysis, the Cui, Hung, and Wang (CHW) procedure (Cui et al. 1999) will be applied to the primary endpoints for the two populations and the secondary endpoints to control the type I error at a one-sided  $\alpha=0.025$  significance level. The CHW method ensures strong control of type I error when the sample size is increased in a data dependent manner. Details about the CHW statistics are provided in Section 6.16.2.4.

If the sample size is increased as a result of the interim analysis, an unadjusted point estimate for both of the primary efficacy analysis will be calculated and reported. A median unbiased point estimate and a stage-wise adjusted confidence interval for the primary efficacy analysis will be calculated and reported based on the approach described by Brannath and colleagues (Brannath et al. 2009) to assess sensitivity of the point estimate.

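### The primary model carries illness severity only as the OS category; adding the Day 1 NEWS, already collected before dosing, would probably bring a modest gain in power

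*SAP*

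**What the plan says.** SAP 6.11.1 states that the primary comparison is "made using logistic regression with baseline stratification factors and treatment group in the model". SAP 6.1.4 defines those factors as age group, region, baseline steroid use and "baseline disease severity (ordinal scale [OS] 4, OS 5, OS 6". SAP 6.2.1 and Protocol 9.4.2 describe the same model. No other baseline measure enters it.

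NEWS is marked for Day 1 in the Schedule of Activities (Protocol 1.3). Protocol 8.1.3.1 says that it "is used to detect and report changes in illness severity in patients with acute illness". It is built from respiratory rate, saturation, temperature, systolic pressure, pulse and consciousness, with an added weight for supplemental oxygen, and is derived from data already entered in the eCRF. On timing, Protocol 8.2.1 says: "The most recent measurements prior to study drug administration will be used to calculate the NEWS". SAP 6.1.2 takes baseline vital signs from the same Day 1 NEWS form: "The baseline of vital signs is defined as the vital signs collated at Day 1".

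In the efficacy tables the NEWS score itself serves only its own mean-change endpoint (SAP Tables KHAA.6.6 and 6.7). Saturation and respiratory rate from the NEWS form also feed a few other endpoints.

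Two SAP rules bear on any added covariate. Section 6.1 excludes from a model any patient who lacks a required covariate. Section 6.4.3 imputes NIAID-OS scores only, within strata of arm, OS and steroid use.

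**The concern.** The primary event is escalation to high-flow oxygen or ventilation, or death, by Day 28. Patients in one OS category can differ widely in respiratory rate, saturation and haemodynamics at entry. Under the current inclusion criterion every entrant needs oxygen, so for those patients the severity term separates OS 5 from OS 6 and nothing finer. If NEWS predicts the event within these strata, adding it would strengthen the primary test without one more patient. SAP 5.2 shows power of 54% in its less favourable scenario, so a few points could matter. The SAP already accepts the principle elsewhere: ANOVA takes the endpoint's baseline value where appropriate (6.2.2), and the repeated-measures model does so too (6.2.6).

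**Working it through.** **1. The plan's own power figures.** For Amendment D (Protocol 9.2: N = 1000, placebo 25%, two-sided 0.05), use power = Φ(d/SE − 1.960), with SE = √(2·p̄(1 − p̄)/500).
- d = 0.05: p̄ = 0.225, SE = 0.02641, d/SE = 1.893, power 47.3% (stated 47%).
- d = 0.075: p̄ = 0.2125, SE = 0.02587, d/SE = 2.899, power 82.6% (stated 83%).

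For Amendment E (SAP 5.2: N = 1400, 75% of alpha to Population 1, 60% on steroids), the 81% and 54% are the power for at least one of two correlated tests. Take α₁ = 0.01875 one-sided, correlation √0.4 and α₂ = 0.00916, solved so that the total is 0.025. With the last stated placebo rate, 25%, this gives 91.6% and 69.4%. A placebo rate of 40% to 45% comes close (80.8% and 56.1%; 78.9% and 54.3%), as does N = 1000 at 25% (80.3% and 54.9%). Amendment E states no placebo rate and cites a custom simulation, so the stated figures are not shown to be wrong. They are also not a base from which to scale a gain.

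**2. Gain for Population 1.** Inputs: N = 1400, 1:1; placebo 25% (Amendment D); two-sided alpha about 0.0495 (99% of 0.05, SAP 6.11.1), critical value 1.964; no missing NEWS. *Assumption:* the part of NEWS not explained by the strata is a standard normal X, with odds ratio per SD of 1.28 to 2.72 (AUC about 0.57 to 0.74). The documents give no value.

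Model: logit P(event) = a + θ·treatment + b·X. Intercepts are set so that the overall event rates stay at 25% and 25% − d. SE(θ) comes from the expected information matrix, and power = Φ(|θ|/SE − 1.964).

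| OR per SD | d = 0.054: θ, SE, ratio | power | d = 0.075: θ, SE, ratio | power |
|---|---|---|---|---|
| 1.00 (no NEWS) | −0.313, 0.129, 2.422 | 67.7% | −0.452, 0.132, 3.415 | 92.7% |
| 1.28 | −0.316, 0.130, 2.435 | 68.1% | −0.457, 0.133, 3.433 | 92.9% |
| 1.65 | −0.326, 0.132, 2.473 | 69.5% | −0.471, 0.135, 3.484 | 93.6% |
| 2.12 | −0.342, 0.135, 2.533 | 71.5% | −0.493, 0.138, 3.564 | 94.5% |
| 2.72 | −0.364, 0.139, 2.609 | 74.1% | −0.524, 0.143, 3.668 | 95.6% |

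The gain is about 0.4 to 6.4 points at 0.054 and 0.2 to 3 points at 0.075.

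**3. What missing NEWS would cost under SAP 6.1.** Dropping a share m of patients multiplies the ratio by √(1 − m), so the gain is cancelled at m = 1 − (ratio without NEWS / ratio with NEWS)². For d = 0.054 and OR 1.65: 1 − (2.422/2.473)² = 4%. Across the four rows it is about 1%, 4%, 8% and 13% to 14%. At OR 1.65 with 5% dropped, power is 67.2% against 67.7% with no NEWS.

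A mean-plus-missing-indicator rule avoids this. In simulation (d = 0.054, 10% missing at random, 4000 runs per cell, Monte Carlo standard error about √(0.7·0.3/4000) = 0.7 points):

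| OR per SD | without NEWS | NEWS with fill-in rule | NEWS, patients dropped |
|---|---|---|---|
| 1.65 | 68.9% | 70.4% | 65.8% |
| 2.12 | 68.0% | 71.8% | 68.1% |

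**4. Population 2.** One per cent of 0.025 is 0.00025 one-sided; the parametric level is slightly higher. Assume Population 2 is 10%, 20% or 30% of 1400 patients, placebo 25% and a 0.075 effect. Power is then 0.8%, 2.5% and 5.4% without NEWS, and 1.0%, 3.3% and 7.1% with NEWS at OR 2.72.

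**The case against.** Adjusting for the stratification factors is conventional and prespecified, and low power is already addressed by the re-estimation to at most 1700 patients (SAP 6.16.2). A gain near the top of the range needs an odds ratio of about 2.7 per SD beyond OS, age, region and steroids. The oxygen weight in NEWS partly repeats OS, and neither the prognostic strength of NEWS nor its completeness on Day 1 is documented. All of this stands, and it limits the point to a low-priority improvement.

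A reader might go further in four ways that the documents do not support.
- **That the gain is free.** The exclusion rule in SAP 6.1 would drop patients without NEWS unless a new rule is written. Protocol 9.4.2 also names the model, so the change has to be documented.
- **That the OS term has only two levels.** Oxygen at entry became a criterion with Amendment D. OS 4 remains a covariate level, a subgroup and part of the endpoint definition, so Population 1 may contain such patients; their share is not given.
- **That 81% and 54% can be rescaled to show the benefit.** They are powers for at least one of two tests under a 75/25 split, since replaced by 99/1.
- **That every test benefits.** Population 2 gains little at its initial level (more only if it is retested at full alpha), and time to recovery and mortality use an unstratified log-rank test.

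**Conclusion.** The omission is confirmed, and it is a missed efficiency rather than an error: the planned test is valid, and no stated power figure relies on NEWS. For Population 1 the likely benefit is modest: about 0.4 to 6.4 points of power for an effect of 0.054 and 0.2 to 3 points for 0.075. These figures rest on an assumed odds ratio per SD of 1.28 to 2.72, a 25% placebo rate, 1400 patients, alpha of about 0.0495 and complete NEWS. With missing values, most of the gain survives only if no patient is dropped.

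**What to change.** Before the study team is unblinded for the primary lock:
- Add baseline NEWS as a linear term, alongside the four stratification factors, to the primary logistic model. Do the same in the NIAID-OS key secondary models that already adjust for covariates (logistic, proportional odds, ANOVA). Leave the log-rank tests unchanged.
- Fill a missing baseline NEWS with the mean for that baseline OS level and add a missing indicator, without using treatment or outcome. State this as an exception to SAP 6.1 so that no patient is excluded.
- Report the stratification-factor-only model as supportive.
- Record the change and its reason in the SAP and study report, and judge under Protocol 9.4 whether it alters a principal feature and so needs an amendment.

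Completeness of Day 1 NEWS and its pooled association with the outcome can be checked in blinded data first; SAP Version 4 already used blinded data to reset the alpha split.

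The cost is SAP text and one covariate derived from data already in the eCRF. The downsides are the missing-value rule, an odds ratio conditional on one more factor, and a covariate that is absent from the Markov imputation model. The last may slightly dilute the gain where outcomes are imputed.
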